6.8 Pharmacokinetic Assessments

Plasma samples for PK analysis will be obtained before and at 0.5, 1, 2, 3, and 4 hours after dosing on Day 1 (prior to receiving the R_01 Knottin tracer) and at 24 hours after dosing (Day 2). A collection window of ± 5 minutes will be allowed for samples up to 1-hour post-dose and a collection window of ± 10 minutes will be allowed for samples that are collected at 2 hours post-dose and after. Samples will be obtained and stored as detailed in the study PK Manual.

The actual collection time of each sample must be recorded in the source data and on the eCRF. If the participant discontinues the study early, a plasma sample for PK should be taken at the Early Termination (ET) Visit if possible.

Aliquots of these PK samples may be used to measure nintedanib and or pirfenidone concentrations in participants receiving these drugs.

6.9 Pharmacodynamic Assessments

6.9.1 PET Imaging

All PET imaging will be performed at prespecified times according to the Schedule of Events (see Appendix 1), using the R₀1 Knottin tracer as synthetized by the Radiology Department at Stanford Medical Center, and following predefined instructions as detailed in the study Radiology Manual.

PET imaging that is performed following administration of PLN-74809 on Day 1 will be conducted as much as possible to coincide with PLN-74809 T_{max} (at least 4 hours post-dose and no more than 30 minutes after the 4 hour PK timepoint) to assess $\alpha_v \beta_6$ receptor occupancy.

Blood samples for radiotracer PK will be obtained at the following time points: 1, 3, 5, 10, 30, and 60 minutes after completion of radiotracer injection for PET-computed tomography (CT) to obtain blood time activity measurements. Each collection time point has a +4-minute window. During some PET-CT scans, sample collection may not be possible or may be obviated due to staffing availability or scientific considerations. Refer to the Radiology Manual for details, including definitive information regarding the allowed sample collection windows.

Confidential Page 307 of 331

6.9.2 HRCT

An HRCT will be performed at Screening only if a scan meeting the quality necessary for diagnosis purposes is not already available. If an HRCT is performed at Screening, a second one is not needed during PET-CT. An HRCT during PET-CT may be performed if the entry HRCT is not adequate for the assessment of HRCT-PET relationship.

6.9.4 Spirometry Testing for FVC Measurement

Spirometry will be performed according to American Thoracic Society (ATS) guidelines and using the Chest Clinic equipment at Stanford Medical Center. FVC will be assessed for all participants at Screening for inclusion criteria purposes.

6.10 Adverse Events Assessments

6.10.1 Timing

In this study, AEs will be collected from the time the participant signs the ICF until the last study visit.

6.10.2 Definition of an Adverse Event

An AE is any event, side effect, or other untoward medical occurrence that occurs in conjunction with the use of a study drug in humans, whether or not considered to have a causal relationship to this treatment. An AE can, therefore, be any unfavorable and unintended sign (that could include a clinically significant abnormal laboratory finding), symptom, or disease temporally associated with the use of a study drug, whether or not considered related to the study drug. Events meeting the definition of an AE include:

Confidential Page 308 of 331

- Exacerbation of a chronic or intermittent preexisting condition including either an increase in frequency and/or intensity of the condition.
- New conditions detected or diagnosed after study drug administration even though it may have been present prior to the start of the study.
- Signs, symptoms, or the clinical sequelae of a suspected interaction.
- Signs, symptoms, or the clinical sequelae of a suspected overdose of either study drug or a concomitant medication (overdose per se will not be reported as an AE/serious adverse event [SAE]). Events that do not meet the definition of an AE include:
 - Medical or surgical procedure (e.g., endoscopy, appendectomy); the condition that leads to the procedure is an AE.
 - Situations where an untoward medical occurrence did not occur (e.g., social and/or convenience admission to a hospital).
 - Anticipated day-to-day fluctuations of preexisting disease(s) or condition(s) present or detected at the start of the study that do not worsen.
- If there is evidence of an AE through report or observation, the Investigator or designee will evaluate further and record the following information:
 - Time of onset and resolution
 - Severity
 - Causality/relation to study treatment
 - Action taken regarding study drug
 - Outcome

6.10.3 Severity of an Adverse Event

Grading the severity of AEs will use the Common Terminology Criteria for Adverse Events (CTCAE) grading system (Version 5.0), as described below. The clinical significance of the AE is determined by the Investigator. The Investigator is encouraged to consult with the Medical Monitor.

Confidential Page 309 of 331

- Grade 1 Mild; asymptomatic or mild symptoms; clinical or diagnostic observations only; intervention not indicated.
- Grade 2 Moderate; minimal, local or noninvasive intervention indicated; limiting age-appropriate instrumental ADL*.
- Grade 3 Severe or medically significant but not immediately life-threatening; hospitalization or prolongation of hospitalization indicated; disabling; limiting self-care ADL**.
- Grade 4 Life-threatening consequences; urgent intervention indicated.
- Grade 5 Death related to AE.

A semi-colon indicates 'or' within the description of the grade.

Common Terminology Criteria for Adverse Events (CTCAE) Version 5.0. Published: November 27, 2017. https://ctep.cancer.gov/protocoldevelopment/electronic_applications/docs/ctcae_v5_quick_reference_8.5x11.pdf

6.10.4 Causal Relationship of an Adverse Event

The Investigator will assess the relationship between study drug and the occurrence of each AE. The Investigator's assessment of the relationship of each AE to study drug will be recorded in the source documents and the eCRF. Alternative causes, such as medical history, concomitant therapy, other risk factors, and the temporal relationship of the event to the study drug should be considered and investigated, if appropriate. The relationship or association of the AE to a study drug (PLN-74809 or placebo) should be assessed using clinical judgment and the following considerations:

- No: Evidence exists that the adverse event has an etiology other than the study drug. For SAEs, an alternative causality must be provided (e.g., preexisting condition, underlying disease, intercurrent illness, or concomitant medication).
- Yes: A temporal relationship exists between the AE onset and administration of the study drug that cannot be readily explained by the participant's clinical state or concomitant therapies. Furthermore, the AE appears with some degree of certainty to be related, based on the known therapeutic and pharmacologic actions or AE profile of the study drug. In case of cessation or reduction of the dose, the AE abates or resolves and reappears upon re-challenge.

Confidential Page 310 of 331

^{*}Instrumental Activities of Daily Living (ADL) refer to preparing meals, shopping for groceries or clothes, using the telephone, managing money, etc.

^{**}Self-care ADL refers to bathing, dressing and undressing, feeding self, using the toilet, or taking medications and not bedridden.

The relationship to study procedures (such as venipuncture) should be assessed using the following considerations:

No: Evidence exists that the AE has an etiology other than the study

procedure

Yes: The AE occurred as a result of protocol-mandated procedures.

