### 6.11.1 Adverse Events

A TEAE is defined as:

- Any AE that has an onset on or after the first dose of study drug.
- Any pre-existing AE that has worsened in severity on or after the first dose of study drug.

AEs will be classified as either related or not related to the study drug. If an AE has missing relationship, it is assumed to be related to the study drug for analysis purposes.

AEs will also be classified as either related or not related to study procedure. If an AE has missing relationship, it is assumed to be related to study procedure for analysis purposes.

Severity of the AE will be graded using the Common Terminology Criteria for Adverse Events (CTCAE) grading system (Version 5.0): Grade 1 (Mild), Grade 2 (Moderate), Grade 3 (Severe), Grade 4 (Life-Threatening), Grade 5 (Death). Grade 3 (Severe) will be assumed for an AE with missing grade.

The following tables will be presented for AEs:

- Number (%) of participants with TEAEs, study drug-related TEAEs, procedure-related TEAEs, serious TEAEs, TEAEs leading to withdrawal, and TEAEs leading to death, by dose and overall.
- Number (%) of participants with TEAEs by system organ class and preferred term, dose and overall.
- Number of events of TEAEs by system organ class and preferred term, dose and overall.
- Number (%) of participants with study drug-related TEAEs by system organ class and preferred term, dose and overall.
- Number (%) of participants with procedure-related TEAEs by system organ class and preferred term, dose and overall.
- Number (%) of participants with TEAEs by system organ class, preferred term, maximum severity, dose and overall.

[figure not shown]
|   |  |                                  |  |
|---|--|----------------------------------|--|
|   |  | Confidentiality Statement |  |
| This document is the property of [REDACTED], and may not be duplicated, copied, altered or removed from company without prior approval from [REDACTED] or in compliance with [REDACTED] |  |                                  |  |

|  |  |                  |                         |
|--|--|------------------|-------------------------|
|  |  | Sponsor:         | Pliant Therapeutics Inc |
|  |  | Protocol Number: | PLN-74809-IPF-201       |
| STATISTICAL ANALYSIS PLAN – PHASE 1 |  |                  |                         |

- [REDACTED]
- [REDACTED]
- Listing of Serious Adverse Events (SAEs) (presented in the Table section of the appendices).

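### The Yes and No causality definitions in Protocol 6.10.4 leave some events in neither category, so drug-related and procedure-related counts may be coded inconsistently

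*Protocol*

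**What the plan says.** Protocol 6.10.4 gives two options for relationship to study drug, to be applied as follows: the relationship "should be assessed using clinical judgment and the following considerations".

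- *No* is defined by "Evidence exists that the adverse event has an etiology other than the study drug". For SAEs it also requires an alternative cause to be named.
- *Yes* opens with "A temporal relationship exists between the AE onset and administration of the study drug that cannot be readily explained by the participant's clinical state" or by concomitant therapies. A second sentence, joined by 'Furthermore', asks for some certainty of a relation "based on the known therapeutic and pharmacologic actions or AE profile of the study drug". A third sentence reads "In case of cessation or reduction of the dose, the AE abates or resolves and reappears upon re-challenge".

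The same section names placebo as a possible study drug, although Protocol 5.1.2 says placebo or control does not apply. A second scale covers study procedures: *No* again needs evidence of another cause, and *Yes* means that the event resulted from a protocol-mandated procedure.

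SAP 6.11.1 keeps the two-way split: "AEs will be classified as either related or not related to the study drug". It adds: "If an AE has missing relationship, it is assumed to be related to the study drug for analysis purposes". A parallel rule covers procedures. The section then plans tables of drug-related and procedure-related TEAEs by dose and overall. Protocol 9.6 also tabulates treatment-related SAEs. The adverse-event endpoint in SAP 3.2 is TEAEs without regard to cause.

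**The concern.** A two-category scale works only if every event belongs in one category. Here each category carries its own positive condition, so an event can fail both. The events most exposed are unexpected ones: they follow a dose, lack another explanation and are not predicted by what is already known. A safety assessment should handle these consistently.

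The study has no control arm, so the investigator's call is the only causal attribution planned. If the definitions do not settle it, the drug-related and procedure-related summaries depend in part on how each assessor resolves the gap. Wording about dose reduction, re-challenge and placebo suggests that the paragraph was not adapted to this trial.

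**Working it through.** The plan states no figure to reproduce. The check is mainly logical, with simple proportions for scale.

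**1. Are the drug categories exhaustive?** Take events in temporal relation to dosing and apply Protocol 6.10.4 as written.

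| Event | Evidence of another cause | Fits known actions or AE profile | *No* met | *Yes* met |
|---|---|---|---|---|
| A | Yes, and it readily explains the event | Either | Yes | No |
| B | None | Yes | No | Yes, subject to the re-challenge sentence |
| C | None | No | No | No |

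Event C meets the first sentence of *Yes* but not the second, and it cannot meet *No*. The categories are not complements.

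**2. Procedure scale.** An event with no evidence of another cause, but not shown to result from a procedure, meets neither definition.

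**3. Fit to the design.** The synopsis gives the duration of treatment as a single dose; Protocol 5.2 allows up to four single doses on different occasions. There is no continuing dosing to stop or reduce. A participant dosed once has no re-exposure, and recurrence can be seen only in those dosed again. SAP section 5 confirms a non-randomized, open-label study.

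**4. What the SAP does with event C.**

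- Entered *Yes*: counted as related.
- Left blank: counted as related.
- Entered *No*: counted as unrelated. No SAP rule revisits it.

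**5. Size.** Protocol 9.2 allows up to 12 participants. If a participant's only related event is the one in the gap, the overall incidence moves by

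1/12 = 8.3 percentage points.

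For context, the exact (Clopper-Pearson) 95% limits are 0 to 26.5% for 0/12 and 0.2 to 38.5% for 1/12. The visible text gives no number per dose. With an assumed 3 participants in a dose column, the shift is 1/3 = 33 points; over an assumed range of 2 to 6 it is 1/2 = 50 down to 1/6 = 16.7 points.

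**6. Direction.** Assume 3 of 12 participants with a truly drug-related TEAE (25.0%).

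- If 0 to 3 of them fall in the gap and are entered *No*, the count runs from 3/12 down to 0/12 (25.0% to 0%).
- If the same events are entered *Yes* or left blank, it stays at 3/12.
- If none of the three is in the gap, but one further participant has a gap event not caused by the drug that is entered *Yes* or left blank, it becomes 4/12 = 33.3%.

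The text does not determine which of these occurs.

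**The case against.** The strongest case against is that the paragraph is guidance, not a checklist. It calls for clinical judgment and labels its contents as considerations, so an assessor facing event C may choose *Yes*, because the timing is unexplained and *No* would need evidence. That is fair, and it defeats any claim that such events cannot be coded. It does not supply a tie-break, so two assessors can code the same event differently and both point to the text.

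A reader might infer that drug-related events will be under-counted. The documents do not support that. *No* has its own evidence requirement, an SAE coded *No* must have a named alternative cause, and a blank is counted as related. Of the three possible entries for a gap event, only one lowers the count.

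Three other strong readings also fail:

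- *Re-challenge is mandatory for* Yes. The sentence is conditional on stopping or reducing the dose. It is ambiguous and ill-suited here, but need not be read as a requirement.
- *Only an already reported reaction can be* Yes. Known pharmacologic actions suffice as an alternative to a known AE profile.
- *This is the first safety look in IPF.* The protocol's contents list ongoing Phase 2 studies whose text is not visible, and exclusion criterion 20 exempts earlier participation with PLN-74809. Prior experience in IPF cannot be ruled out.

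It is also true that no event disappears through its causality code. All TEAEs are tabulated, all AEs are listed, and at most 12 participants can be reviewed one by one. This limits the consequence to the relatedness summaries. Finally, the 8.3-point step applies to any yes/no output in 12 people: it shows scale, not that misclassification will happen.

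**Conclusion.** The point holds in a limited form. As written, both causality scales leave some events without a category, and the cessation, re-challenge and placebo wording does not fit an uncontrolled study of single doses. Coding of gap events may therefore be inconsistent, in either direction. The effect is confined to the drug-related and procedure-related TEAE summaries and the treatment-related SAE counts; for SAEs the named-alternative rule narrows it further. The all-TEAE endpoint is untouched.

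The 8.3-point step rests on full enrolment of 12 and on the reclassified event being that participant's only related one. The per-dose shifts rest on assumed column sizes. How many events would fall in the gap cannot be derived from the documents.

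**What to change.** In Protocol 6.10.4, redefine both scales so that every event has one answer:

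- *Yes*: there is a reasonable possibility that the study drug (or, on the second scale, the study procedure) caused the event.
- *No*: there is no reasonable possibility.

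State that timing, alternative causes, known actions or AE profile, and any recurrence at a later dose are supportive considerations and not conditions for either answer; the cessation and re-challenge sentence then no longer stands as part of *Yes*. Keep the requirement to name an alternative cause for an SAE coded *No*. Delete the reference to placebo. SAP 6.11.1 can stay as it is, including its rule for missing relationships.

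The cost is one protocol paragraph and matching eCRF completion guidance. The small downside is that the reported related incidence may be somewhat higher.

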6.10.5 Outcome

The outcome of an AE will be recorded on the AE eCRF as follows:

- Recovered / Resolved
- Recovering / Resolving
- Recovered / Resolved with Sequelae
- Not Recovered / Not Resolving
- Fatal
- Unknown

6.10.6 Pregnancy

A pregnancy is not an AE. If a female participant or the female partner of a male study participant becomes pregnant while enrolled in the study following administration of study drug or within 90 days after last dose, the Sponsor must be notified within 24 hours of the Investigator learning of the pregnancy. The participant or the female partner of a male study participant will be followed through the outcome of the pregnancy. The Investigator is required to provide all the relevant information to the Sponsor using the Pregnancy Information Form to do so.

6.10.7 Clinical Laboratory Adverse Events

Abnormal laboratory findings (e.g., clinical chemistry, hematology, urinalysis) or other abnormal assessments per se are not reported as AEs. However, those abnormal findings that are deemed clinically significant or that are associated with signs and/or symptoms must be recorded as AEs if they meet the definition of an AE (or recorded as an SAE if they meet the criteria of being serious), as described in Section 6.10.2. Clinically significant abnormal laboratory or other abnormal findings that are detected after consent or that are present at Baseline and worsen after consent are included as AEs (and SAEs if serious).

The Investigator should exercise his/her medical and scientific judgment in deciding whether an abnormal laboratory finding or other abnormal assessment is clinically significant. Usually, the abnormality should be associated with a clinically evident sign or symptom, or

Confidential Page 311 of 331

be likely to result in an evident sign or symptom in the near term, to be considered clinically significant. A clinically significant laboratory abnormality in the absence of clinical symptoms may jeopardize the participant and may require intervention to prevent immediate consequences. For example, a markedly low serum glucose concentration may not be accompanied by coma or convulsions, yet be of a magnitude to require glucose administration to prevent such sequelae.

6.10.8 Serious Adverse Events

6.10.8.1 Definition of Serious Adverse Events

An SAE is any untoward medical occurrence that at any dose:

- Is life-threatening
- Results in death
- Requires inpatient hospitalization (i.e., admission, overnight stay) or prolongs existing hospitalization
- Results in persistent or significant disability/incapacity, or
- Is a congenital anomaly/birth defect

An AE is considered life-threatening if, in the opinion of either the Investigator or the Sponsor, its occurrence places the participant at immediate risk of death. It does not include an AE that, had it occurred in a more severe form, might have caused death.

Important medical events that are not one of the above may be considered to be SAEs by the Investigator when, based upon appropriate medical judgement, they are considered to be clinically significant and may jeopardize the participant or when medical or surgical intervention may be required to prevent one of the outcomes listed above. (Examples of such events include allergic bronchospasm requiring intensive treatment at an emergency room or at home, blood dyscrasias, convulsions that do not result in inpatient hospitalization, or the development of drug dependency or drug abuse.)

6.10.8.2 Reporting Serious Adverse Events

In order to meet the requirements for expedited reporting of SAEs meeting specific requirements to applicable regulatory authorities and IRBs, all SAEs must be reported to the Sponsor within 24 hours from the time site personnel first become aware of the event. This may be initially achieved by telephone or by completing an SAE report form and e-mailing it to the email address, as provided on the form.

Initial notification of an SAE by telephone must be confirmed in writing 24 hours from the time the site investigational team first become aware of the event using the serious adverse event report form as described above. As further information regarding the SAE becomes available, such follow up information should be documented on a new SAE report form, marked as a follow-up report, and scanned and e-mailed to the address provided.

Confidential Page 312 of 331

Withdrawal from the study in the event of a SAE and therapeutic measures taken shall be at the discretion of the Investigator. A full explanation for the discontinuation from the study should be made in the eCRF.

The reporting of any SAEs to applicable regulatory authorities will be the responsibility of the Sponsor in compliance with applicable country regulations. All SAEs must be reported to the IRB by the Investigator in accordance with their regulations.

6.11 Removal of Participants from the Study or Discontinuation of Study Drug

In accordance with the Declaration of Helsinki, participants have the right to withdraw from the study at any time for any reason. The Investigator or Sponsor may withdraw a participant from the study or discontinue study drug for any of the following reasons:

- Noncompliance with protocol procedures, including those relating to administration of study drug.
- A serious or intolerable adverse event occurs.
- A clinically significant change in a laboratory parameter occurs.
- The Sponsor or Investigator terminates the study.
- The participant requests to be discontinued from the study.

If a participant is withdrawn from the study or discontinues study drug, he or she will undergo ET assessments (refer to the Schedule of Evaluations in Appendix 1).

